8.2 Metformin

8.2.1 Other names

Glucophage, N,N-dimethylimidodicarbonimidic diamide hydrochloride

8.2.2 Classification - type of agent

Oral antihyperglycemic drugs

8.2.3 Mode of action

Metformin is classified as an antidiabetic agent, a biguanide derivative. It decreases hepatic glucose production, decreases intestinal absorption of glucose, and improves insulin sensitivity by increasing peripheral glucose uptake and utilization. More recent data has revealed an immunomodulatory effect on cancer cells as described in section 1.2.

8.2.4 Storage and stability

Store at 20°–25° C (68°–77° F); excursions permitted to 15°–30° C (59°–86° F). [See USP Controlled Room Temperature.] Product will be dispensed in light-resistant containers.

8.2.5 Protocol dose specifics

Extended formulation of 500 mg tablets will be used. Metformin will be initiated during a 7-day Induction period at 1,000mg orally once daily. Metformin will then be escalated by 500mg every 7 days as tolerated (C1D1 and C1D8) until the full 2,000mg dose is reached.

8.2.6 Preparation

None

8.2.7 Route of administration for this study

Oral

8.2.8 Incompatibilities

No formal drug-drug interactions have been reported with metformin and PD-1 or PD-L1 inhibitors.

- Cephalexin: May increase the serum concentration of metformin.
- Cimetidine: May decrease the excretion of metformin.
- Corticosteroids (systemic): May diminish the hypoglycemic effect of antidiabetic agents. In some instances, corticosteroid-mediated HPA axis suppression has led to episodes of acute adrenal crisis, which may manifest as enhanced hypoglycemia, particularly in the setting of insulin or other antidiabetic agent use.
- Iodinated Contrast Agents: May enhance the adverse/toxic effect of metformin. Renal dysfunction that may be caused by iodinated contrast agents may lead to metformin-associated lactic acidosis. Use of these agents should be avoided while patients are receiving metformin and for 48 hours after discontinuation; if it is necessary to conduct imaging while taking metformin, it should be performed with adequate hydration, and the use of mucomyst may be considered.

8.2.9 Availability & Supply

As of January 2019, BMS will not provide Extended release Metformin tablets for the study. We will be switching from metformin supplied by BMS, to commercial supply of metformin which will be purchased and distributed through Northwestern University's investigational pharmacy.

It will be handled as an investigational agent and dispensed by the Investigational Pharmacy.

8.2.10 Side effects

Frequent (>10%)

Diarrhea, nausea, and flatulence. These side effects typically subside after continued use of the medicine.

Less Frequent (≤ 10%)

Asthenia, Indigestion, abdominal discomfort and Headache

Rare and serious

A rare severe side effect is lactic acidosis (1 in 33,000 patients). The symptoms of lactic acidosis included feeling very weak, tired, or uncomfortable, unusual muscle pain, trouble breathing, unusual or unexpected stomach discomfort, feeling cold, feeling dizzy or lightheaded, and suddenly developing a slow or irregular heartbeat.

8.2.11 Nursing implications

Administer with food (to decrease GI upset) and with a full glass of water when feasible. Monitor bicarbonate levels on chemistry panels to ensure they stay within the normal range per institution.

8.2.12 Return and Retention of Study Drug

Unused metformin, dispensed during previous visits, must be returned and drug accountability records updated. Returned capsules must be discarded and cannot be re-used in this study or outside the study.

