4.0 TREATMENT PLAN

4.1 Overview

Nivolumab and metformin combination will be administered intravenously and orally, respectively, until disease progression or intolerable toxicity. Metformin will be initiated during a 7-day Induction period at 1,000mg orally once daily. Metformin will then be escalated by 500mg every 7 days as tolerated (C1D1 and C1D8) until the full 2,000mg dose is reached. Extended release formulation - Glucophage XR will be used for the study and commercial supply will be used which will be purchased and dispensed by NU investigational pharmacy. During Cycle 1-4 (1 cycle = 28 days), nivolumab will be given at 240mg every 14 days (Day 1 & 15) over approximately 30 minutes (-5 / +15 minutes). Starting with Cycle 5 Day 1, nivolumab will be given at 480mg IV every 28 days over approximately 60 minutes (-10 / +15 minutes). Patients will be assessed for response every 8 weeks (2 cycles).

Note: Please refer to section 4.4 for patients who may continue treatment after initial progression.

Dosing schedule is summarized in the table below.

Table 4-1: Dosing of Nivolumab and Metformin

Drug	Dose	Route	Schedule
Nivolumab (Opdivo)	C1-4: 240mg C5+: 480mg	IV	Cycle 1-4: every 14 days Cycle 5+: every 28 days until progression of disease, intolerable toxicity, or withdrawal of consent
Metformin hydrochloride (Glucophage XR)	2,000mg*	PO	daily with evening meal until progression of disease, intolerable toxicity, or withdrawal of consent 
 • starting dose: 1,000mg • dose escalation plan: weekly by 500mg

*Metformin will be initiated at 1,000mg during the Induction period and escalate by 500mg (1 tablet) every 7 days until the final dose of 2,000mg.

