4.2.2 Metformin

Metformin will be administered orally once daily until disease progression, intolerable toxicity or withdrawal of consent. Extended release formulation - Glucophage XR, 500 mg will be used for the study. Two tablets (1,000 mg) PO once daily will be given for the first 7 days, then 3 tablets (1,500 mg) for the next 7 days, then 4 tablets (2,000 mg) for the rest of the treatment period. Metformin should be taken with meals. This dose escalation plan is to minimize possible gastrointestinal toxicity of metformin. 2550mg of metformin is the FDA approved maximum dose of metformin. Tablets should not be cut, crushed, or chewed. Metformin will be held per institutional guidelines with IV contrast dye injection required for each imaging studies. Metformin dosing can occur independently of nivolumab dosing. No premedications are needed.

Patients will maintain a drug diary throughout the study to monitor compliance of metformin dosing. Patients will return completed drug diaries, drug bottles, and any unused metformin tablets at each study visit.

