5.0 STUDY PROCEDURES TABLE

Table 5-1: Study Procedures

STUDY PROCEDURES	Screening ^{2,10}	Induction ¹⁵ (7 days)	Cycle 1-4 (Cycle=28 days)		Cycle 5+ (Cycle = 28 days)	End of Treatment ¹³ ± 7 days	Follow Up ¹⁶
			D1	D1 (±3 day)			
Study window							
Informed Consent ¹	X						
Medical history	X				X		
Physical Exam	X	X	X	X	X	X	
Vital signs ³	X	X	X	X	X	X	
ECOG PS	X	X	X	X	X	X	
AE reporting		X	X	X	X	X	X
Concomitant Medications	X	X	X	X	X	X	
Chemistry panel ⁴	X	X	X	X	X	X	
CBC with differential ⁵	X	X	X	X	X	X	
Pregnancy test ⁶	X		X				X
Thyroid function test ⁷	X						
ECHO/ECG	X ¹⁷						
Imaging (CT or MRI) ⁸	X		X ⁸		X ⁷		
Biopsy tissue ^{9,14}	X						
Blood biomarker ¹⁴		X	X ¹⁴				X
Nivolumab infusion ¹¹			X ¹¹	X ¹¹	X ¹¹		
Metformin dispensing ¹²		X	X		X		
Survival							X

1. Informed consent must be signed within 30 days of registration. If signature is outside that window a new consent should be signed.
2. Pre-study H&P and all labs must be ≤ 14 days before registration. Tumor measurements and radiologic evaluations must be ≤28 days before registration.
3. Vital signs include pulse, blood pressure, and weight. Height will be recorded at baseline only.
4. Serum Chemistry will include calcium, chloride, magnesium, phosphorus, creatinine, sodium, potassium, blood urea nitrogen, bicarbonate, glucose, total bilirubin, aspartate aminotransferase (AST), alanine aminotransferase (ALT), alkaline phosphatase (ALP), albumin, and total protein.
5. CBC: Performed at each study visit, prior to nivolumab. For patients experiencing significant drop in WBCs or platelets felt related to treatment, CBCs should be obtained more frequently (weekly or more frequently) to assess timing for retreatment or need for transfusion support.

6. Serum or urine test only for women of childbearing potential; must be tested within 7 days prior to registration and on Cycle 1 Day 1 (prior to nivolumab).
7. Thyroid function tests will include thyroid stimulating hormone and free T4. This will be done at baseline then only as clinically indicated thereafter.

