8. The same modality used at baseline should be used throughout for imaging. CT imaging with contrast will occur every 2 cycles starting with Cycle 3 Day 1 (\pm 7 days) and should include chest, abdomen, and pelvis. Neck will be included only if measurable lesions are present. Metformin should be held prior to scans per each institutional protocol. Tumor measurements will be performed using RECIST 1.1. Progressive Disease (PD) must be confirmed by repeat scan within 8 weeks at least after 4 weeks. Patients with a known history of CNS disease must have CNS imaging at screening to rule out activity.
9. Patients will undergo a fresh tissue biopsy prior to study enrollment, unless deemed to be clinically inappropriate per PI. If not feasible, archived tissue will be used (if available).
10. The maximum time interval between registration and the first dose of study drug will be 14 days
11. Nivolumab will be given as follows:
Cycle 1-4: 240mg IV over 30 minutes (-5 / +15 minutes) every 14 days (Day 1 & 15, \pm 3 days)
Cycle 5+: 480mg IV over 60 minutes (-10 / +15 minutes) every 28 days (Day 1, \pm 3 days) until disease progression, intolerance, or withdrawal of consent.
12. Metformin will be dispensed Day 1 of each cycle. Dosing will begin at 1,000mg po once daily and escalate by 500mg every 7 days until the final dose of 2,000mg is reached. Patients will return unused drug and drug bottles at each study visit and will maintain a drug diary to track compliance.
13. The end of treatment visit should occur 30 days after the last dose of study treatment (+/- 7 days) or before starting another line of treatment, whichever comes first.
14. Correlatives from peripheral blood will be collected for all patients at Induction Day 1, C1D1, C3D1, and at the EOT. Biopsy samples (fresh or archived) will be collected for all patients if possible. See separate lab manual for specifications. See section 9.0 for details.
15. Metformin monotherapy will be given at 1,000mg PO QD during the 7-day Induction period, prior to starting nivolumab on Cycle 1 Day 1.
16. After patients come off treatment they will be followed up at 3, 6, 9, and 12 months (\pm 7 days) and then every 6 months (\pm 14 days) for 3 years for survival and progression of disease via either clinic visits or phone calls.

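### The metformin return, discard and dispensing rules, followed literally, contradict continuous daily dosing by leaving Days 15-28 of Cycles 1-4 without a scheduled supply

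*Combined protocol and SAP*

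**What the plan says.** **Return.** Section 4.2.2: "Patients will return completed drug diaries, drug bottles, and any unused metformin tablets at each study visit". Footnote 12 of Table 5-1 repeats it: "Patients will return unused drug and drug bottles at each study visit".

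**Fate of returned drug.** Section 8.2.12: "Unused metformin, dispensed during previous visits, must be returned and drug accountability records updated", followed by "Returned capsules must be discarded and cannot be re-used in this study or outside the study".

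**Supply.** Footnote 12: "Metformin will be dispensed Day 1 of each cycle". The metformin row of Table 5-1 marks Induction, Day 1 of Cycles 1-4, and Cycle 5 onward. The second Cycle 1-4 column is blank in that row.

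**Visits.** Section 4.1: "During Cycle 1-4 (1 cycle = 28 days), nivolumab will be given at 240mg every 14 days (Day 1 & 15"). Footnote 11 has the same two infusion days. Footnote 5 links study visits to infusions: "CBC: Performed at each study visit, prior to nivolumab". Physical examination, vital signs, laboratory tests and adverse event review are marked in both Cycle 1-4 columns.

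**Dosing.** Table 4-1 and Section 4.2.2 have metformin taken daily until progression, unacceptable toxicity or withdrawal, at four 500 mg tablets a day once the two lower weekly steps are complete.

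**The concern.** Metformin is the component under test in both arms. Day 15 of Cycles 1-4 is a study visit by the protocol's own markings. A patient who follows the text brings back the tablets meant for the second half of the cycle, the pharmacy must destroy them, and the next scheduled dispensing is 14 days away. Daily dosing then cannot be carried out. To keep the patient on daily metformin, staff must depart from the return rule or the discard rule, or dispense at a visit where none is scheduled, although Section 11.6 asks for conduct as written.

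If the accountability text were followed even in part, a low objective response rate would be harder to read, because weak activity of the combination could not be cleanly separated from missing metformin. Section 10.3 defines the primary analysis set irrespective of exposure and specifies no compliance or exposure analysis. The Cycle 3 Day 1 blood sample, which Section 9.3.4 uses for markers of response to metformin, would also fall at the end of an unsupplied fortnight.

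**Working it through.** The plan gives no figure on this point to reproduce. The check counts days and tablets from the plan's own schedule.

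**Inputs**
- Cycle length 28 days; visits on Days 1 and 15 in Cycles 1-4 (Section 4.1, footnote 11).
- Metformin 1,000 mg/day for 7 induction days, 1,500 mg/day on Cycle 1 Days 1-7, then 2,000 mg/day (Sections 4.1 and 4.2.2); 500 mg tablets.
- Dispensing at Induction and on Day 1 of each cycle (Table 5-1, footnote 12).
- Scans every 2 cycles from Cycle 3 Day 1, ±7 days (footnote 8), so the first two are at Cycle 3 Day 1 and Cycle 5 Day 1.

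**Days without supply, literal reading**
- Per cycle: 28 − 14 = 14 days (Days 15-28).
- Cycles 1-4: 4 × 14 = 56 of 4 × 28 = 112 days (50%).
- Relative to the 24-week time point in Section 10.1: 56 of 168 days, or one third.

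**Cumulative dose through Cycle 4, including induction**
- Scheduled: 7×1,000 + 7×1,500 + 21×2,000 + 84×2,000 = 7,000 + 10,500 + 42,000 + 168,000 = 227,500 mg.
- Literal: 7×1,000 + 7×1,500 + 7×2,000 + 3×14×2,000 = 7,000 + 10,500 + 14,000 + 84,000 = 115,500 mg.
- Ratio: 115.5 / 227.5 = 0.508.

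**Tablets in Cycles 1-4 only**
- Scheduled: 105 + 3 × 112 = 441.
- Surrendered at each Day 15: 14 × 4 = 56, so 4 × 56 = 224 in all.
- Remaining: 441 − 224 = 217, or 49%.

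**Position relative to scans**
- An on-time scan at Cycle 3 Day 1 or Cycle 5 Day 1 follows 14 unsupplied days.
- At either end of the ±7-day window, 7 of the preceding 14 days are unsupplied.

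**Where the gap does not arise**
- Induction drug returned on Cycle 1 Day 1 is replaced that day.
- From Cycle 5 the only scheduled visit is Day 1, when drug is both returned and dispensed.

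The column headings of Table 5-1 are damaged in the text copy. The second Cycle 1-4 column is identified as Day 15 from footnote 11, which gives infusions "every 14 days (Day 1 & 15". Footnote 12 carries the dispensing rule independently of the table.

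**The case against.** The best reply is that the protocol, read as a whole, does not prescribe a break. No section orders one, and the daily-dosing rule stands in the same section as the return rule, so a patient without drug on Days 15-28 would be off protocol. That is right, and it fixes what the point is: return, discard and Day 1 dispensing can all be obeyed together, and the conflict is between those three rules and continuous dosing.

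Second, a sensible reading removes the gap. Diary, bottles and tablets come back together as a compliance check. *Unused* can mean left over from a finished supply, and the ban on re-use can mean only that returned stock must not be re-dispensed. The step up at Cycle 1 Day 8 has no visit in Table 5-1, so patients are plainly expected to hold drug at home across a dose change. Footnote 12 does not say that metformin is dispensed on Day 1 alone, and it does not forbid dispensing at Day 15. All of this stands, and it makes a full loss unlikely. It does not remove the defect: both return rules apply to every study visit, and at Day 15 the Day 1 supply is drug dispensed at a previous visit within the meaning of Section 8.2.12.

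Third, diaries and tablet counts would show a two-week gap at the next visit, and Section 10.3 does not bar exposure reporting. That also stands. The position just before scans should not be pressed either, since metformin may in any case be held around contrast imaging.

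A reader might go further and infer that most responses would appear in the affected window, or that sites would differ in practice. The documents support neither. They give no distribution of response times. The trial is planned as a single-institution study with one investigational pharmacy, and other institutions are mentioned only as a possibility.

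**Conclusion.** The contradiction is real and the text is wrong as written. The size, 56 of 112 days and 115.5 g of 227.5 g through Cycle 4, is an upper bound. It assumes that every patient surrenders all remaining tablets at every Day 15 visit of Cycles 1-4, that the tablets are destroyed, that nothing is issued before the next Day 1, and that scheduled doses are otherwise taken in full.

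It would be tempting to conclude that patients will receive half their metformin, or that the primary endpoint is biased by a known amount. The documents do not support this: they require daily dosing, leave room for a workable reading, and give nothing from which to estimate an effect on response rate. The supported conclusion is narrower. The accountability text, if obeyed, interrupts the experimental drug, and it can be corrected at almost no cost.

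**What to change.** Reconcile Sections 4.1, 4.2.2 and 8.2.12, the metformin row of Table 5-1 and footnote 12, so that the visits at which metformin is surrendered and discarded are the visits at which it is dispensed, and the result agrees with the dosing text. The sponsor chooses how: for example, a tablet count without surrender at Day 15, or dispensing listed at every surrender visit. Replace *capsules* with tablets in Section 8.2.12.

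The cost is one wording amendment and a matching pharmacy instruction. No patients, procedures or analyses are added, and no dose or clinical rule is proposed.

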8.3 Combination of metformin and nivolumab

8.3.1 Side Effects when nivolumab and metformin are given together

To our knowledge, no clinical trials combining metformin and nivolumab have been reported. Therefore, the side effects will be carefully monitored during the study.

9.0 CORRELATIVES/SPECIAL STUDIES

A fresh tissue biopsy of the primary tumor or a metastatic site at baseline will be collected if possible. If not feasible archived tissue will be used (if available). Fresh tissue biopsies will be performed using an image-guided core needle according to institutional practice. Tumor samples will be stored and may be used for additional correlative studies at a later date such as, but not limited to, immunohistochemistry, tumor mutation analysis, and proteomic analysis.

9.1 Sample Collection Guidelines

Blood samples are mandatory and will be collected for Flow and Biomarker analysis at Induction Day 1, C1D1, C3D1, and EOT.

9.2 Sample Processing, Storage, and Shipment

Refer to the lab manual for sample processing, storage, and shipment information.

9.3 Assay Methodology

9.3.1 PD-L1 immunohistochemistry

Formalin-fixed, paraffin-embedded tumor specimens will be stained with anti-PD-L1 monoclonal antibodies. PD-L1 will be scored as a percentage by two independent pathologists who are unaware of clinical data. PD-L1 staining as a predictive measure will be explored at various thresholds of positivity.

NU Study Number: NU 16L04
Other Study Number: CA 209-801

9.3.2 Tumor infiltrating lymphocytes

TILs (CD8+, CD4+, nuclear FOXP3+) will be quantified by immunohistochemistry and assessed on hematoxylin and eosin stained tumor sections. TIL subsets will be classified as intraepithelial (iTILs) or stromal (sTILs), where iTILs are defined as the percentage of lymphocytes in direct contact with tumor cells, and sTILs are defined as the percentage of lymphocytes relative to the tumor stroma. Scoring, as a continuous percentage, will be performed by two independent pathologists who are unaware of clinical data.

9.3.3 T cell subpopulations

Population of CD4+, CD8+, and regulatory T cells (CD4+/CD25+) will be counted by cell sorting of PBMCs. Expression of CD4, CD8, and FOXP3 will be also examined in the tumor tissues to estimate relative ratio between T helper cells, killer T cells, and regulatory T cells.

9.3.4 Immune and Genomic Biomarkers

To assess the dynamic change in both immune and genomic biomarkers in blood that may correlate with response to metformin. Blood will be collected prior to starting metformin, pre-dose on C1D1, C3D1, and EOT.

9.4 Specimen Banking

Patient samples collected for this study will be retained at Robert H Lurie Cancer Center of Northwestern University Pathology Core Facility. Specimens will be stored indefinitely or until they are used up, and such samples may be shared with researchers at other institutions. If future use is denied or withdrawn by the patient, best efforts will be made to stop any additional studies and to destroy the specimens.

[name] will be responsible for reviewing and approving requests for clinical specimen from potential research collaborators outside of Northwestern University. Collaborators will be required to complete an agreement (a Material Transfer Agreement or recharge agreement) that states specimens will only be released for use in disclosed research. Any data obtained from the use of clinical specimen will be the property of Northwestern University for publication and any licensing agreement will be strictly adhered to.

The following information obtained from the subject's medical record may be provided to research collaborators when specimens are made available:

- Diagnosis
- Collection time in relation to study treatment
- Clinical outcome – if available
- Demographic data

10.0 STATISTICAL CONSIDERATIONS

10.1 Study Design/Study Endpoints

This will be a phase II study of nivolumab and metformin in patients with advanced non-small cell lung cancer.

The **primary endpoint** is **objective response rate** (ORR, complete response and partial response) using RECIST criteria v1.1 measured at 24 weeks from the start of treatment.

Secondary endpoints include assessing the efficacy of the combination treatment of nivolumab and metformin according to ORR, DCR, PFS, and OS in the above population using immune-related RECIST criteria (irRECIST) criteria in addition to RECIST criteria, and to assess the safety and tolerability profile of the combination treatment of nivolumab and metformin using CTCAE version 4.

NU Study Number: NU 16L04
Other Study Number: CA 209-801

Exploratory endpoints include biomarkers predictive of response from tissue and/or blood. They include but are not limited to assessment of tissue-based immunohistochemical expression of PD-L1; TILs; peripheral T cell subpopulations.

Clinical outcome will be analyzed according to three levels of PD-L1 expression: <1%, 1-50%, and >50%.

Patients in Arm B (those who received prior PD-L1) will be categorized into two groups:

1. Those who progressed while taking prior PD-L1 therapy ("checkpoint failures")
2. Those who responded to and failed or recurred after coming off PD-L1 therapy

